Based on the approved dose of blonanserin tablet, the initial dose of DSP-5423 (tablet) was set at 8 mg/day and the dose was increased or decreased according to the maintenance dose (8-16 mg/day). Oral administration was planned after meal (in the morning and in the evening) in accordance with the approved treatment regimen of blonanserin tablet.

Since initial dose was set at 8 mg/day, it was considered necessary to determine the optimal dose

for 2 weeks. It has been reported that the treatment response assessment of antipsychotics should be performed 2 to 4 weeks after administration initiation ^{ref 11)}. Furthermore, in the clinical studies of DSP-5423 (tablets) conducted in Japan, most of the common/frequent adverse events, including akathisia, tremors, insomnia, and increased blood prolactin, have been observed in 4 weeks after administration initiation. Therefore, 6-week was set as the duration enough to collect effectiveness and safety data on DSP-5423 (tablet).

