8.2 Exclusion criteria

Exclusion from this clinical study if any of the following applies:

- 1) Patients in a coma
- 2) Patients under the strong influence of central nervous system depressants such as barbituric acid derivatives
- 3) Patients receiving treatment with adrenaline, azole antifungals (excluding drugs for topical use), or human immunodeficiency virus (HIV) protease inhibitors.
- 4) Patients with medical history of hypersensitivity to bronanserin

- 5) Patients with a history of or current neuroleptic malignant syndromes, tardive dyskinesia or water intoxication
- 6) Patient with Parkinson's disease
- 7) Patients with active suicidal ideation or those with a suicide attempt history who are considered ineligible for the study by the Investigator
- 8) Patients with an HbA1c level (NGSP level) of 8.4% or higher
- 9) Patients with physical exhaustion accompanied by conditions such as dehydration or malnutrition
- 10) Patients with a history of or complication(s) involving serious cardiovascular, hepatic, renal, organic brain, hematologic, endocrine, convulsive disease or other conditions, and who are considered ineligible for the study by the Investigator
- 11) Patients with skin injuries, skin disease, or tattoos at the site of application (back, chest, or abdomen) that precludes adequate patch placement.
- 12) Patients with a history of drug abuse, drug dependency, alcohol abuse, or alcohol dependency within 6 months (180 days) before screening
- 13) Patients who received any depot preparation (sustained-release formulation) of antipsychotics within 3 months (90 days) before screening
- 14) Patients who received clozapine administration within 4 months (120 days) before screening
- 15) Patients who received administration of blonanserin within 1 Year (365 days) prior to screening and were considered resistant to treatment for blonanserin
- 16) Patients who received monoamine oxidase (MAO) inhibitor administration within 1 month (30 days) before screening
- 17) Patients who received electroconvulsive therapy within 6 months (180 days) before screening
- 18) Pregnant or nursing mother
- 19) Patients with a history or complication(s) of hypersensitivity to two or more drugs (patients with a history or complication(s) of drug-induced allergic reactions such as anaphylaxis, rash, and urticaria)
- 20) Patients with medical history or complication(s) of malignant tumor within 5 Years before screening
- 21) HIV-infected patients

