10.3.4 Medications for complications

All drugs used for the treatment for complications (eg, hypertension, hyperlipidemia, diabetes) at screening should be continued without any dosage modification as much as possible from beginning of study drug administration/application until the last visit (Visit 113) of DSP-5423P application period or the discontinuation visit. If the complications worsen or improve, the dosage of the concomitant drugs for these complications may be changed accordingly.

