8.4 Baseline

Baseline value for analysis (for the DSP-5423P treatment period) is defined as the last non-missing data on or prior to Day 1.

Regarding to Cohort 1, baseline value for the DSP-5423 (tablet) administration period (Tab-Baseline) is defined as the last non-missing data on or prior to the day of initial administration of DSP-5423(tablet).

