9.12.2 Laboratory test

Observed values and changes from baseline at DSP-5423P application period for the hematology, and blood chemistry parameters will be summarized by visits including LOCF endpoints. For urinalysis parameters, the number and percentage of subjects in each category of parameters will be summarized at baseline of DSP-5423P application period, each visit, and LOCF endpoint. All laboratory parameters and any abnormal laboratory values, which are all values beyond its own normal range at least one time whenever in DSP-5423P application period, will be listed respectively.

Criteria for Markedly Abnormal Post-Baseline Laboratory Values(MAPLV) for abnormal values in the hematology, and blood chemistry parameter can be found in Table 6. The frequencies and percentages of subjects who met MAPLV at least once in the post-baseline of DSP-5423P (including unscheduled visits), will be presented.

Table 6 Criteria for Markedly Abnormal Post-Baseline Laboratory Values

Hematology Parameter	Markedly Abnormal Range
Hemoglobin	Male: ≤ 11.5 g/dL
	Female: ≤ 9.5 g/dL
Hematocrit	Male: $\leq 37\%$
	Female: $\leq 32\%$
WBC	$\leq 2.8 \times 10^3/\mu\text{L}$
	$\geq 16 \times 10^3/\mu\text{L}$
Platelets	$\leq 75 \times 10^3/\mu\text{L}$
	$\geq 700 \times 10^3/\mu\text{L}$
Chemistry Parameter	Markedly Abnormal Range
ALT	$\geq 3 \times \text{ULN}$
AST	$\geq 3 \times \text{ULN}$
Alkaline Phosphatase	$\geq 1.5 \times \text{ULN}$
Na/Sodium	$\leq 130 \text{ mEq/L}$

	> 150 mEq/L
K/Potassium	< 3 mEq/L
	> 5.5 mEq/L
Cl/Chloride	< 90 mEq/L
	> 115 mEq/L
Blood Glucose (fasting)	< 50 mg/dL
	> 250 mg/dL
HbA1c	>= 7.5%
Total Bilirubin	> 2 x ULN
Blood Urea Nitrogen	> 30 mg/dL
Creatinine	> 2.0 mg/dL
CK	> 3 x ULN
Serum Prolactin	>= 5 x ULN
Triglycerides (fasting)	> 300 mg/dL
Total Cholesterol (fasting)	> 300 mg/dL

Note: A value is considered MAPLV if it is outside the Markedly Abnormal Range.

Note: Blood glucose, triglycerides, and total cholesterol are limited for blood samples collected in fasting state.

Box plot of observed value of the hematology and blood chemistry parameters will be provided by visits including baseline of DSP-5423P application period and LOCF endpoint.

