The number and percentage of subjects met have QTcB or QTcF criteria in Table 8 will be summarized. The ECG parameters for subjects who met the criteria in Table 8 at least once in the DSP-5423P post-baseline (including unscheduled visits) will be listed.

Table 8 QT Prolongation

QTc Prolongation
QTc > 450 msec
QTc > 480 msec
QTc > 500 msec
Increased from baseline > 30 msec
Increased from baseline > 60 msec

For DSP-5423(tablet) treatment period in Cohort 1, observed values and changes from baseline in DSP-5423(tablet) treatment period for the ECG parameters will be summarized by visits including LOCF endpoints.

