9.12.6 C-SSRS

C-SSRS will be summarized for each cohort and cohort total, and baseline for Cohort 1 is defined as baseline at DSP-5423(tablet) treatment period and one for Cohort 2 is defined as baseline at DSP-5423P application period.

For ‘Suicidal ideation’, the number and percentage of subjects by items, with any suicidal ideation, with no suicidal ideation, with serious suicidal ideation defined as ‘Yes’ in item 4 or item 5, will be summarized at baseline, each visit, entire DSP-5423(tablet) treatment period, and entire DSP-5423P application period.

Suicidal ideation

1. Wish to be dead
2. Non-specific active suicidal thoughts
3. Active suicidal ideation with any methods [not plan] without intent to act
4. Active suicidal ideation with some intent to act, without specific plan
5. Active suicidal ideation with specific plan and intent

For ‘Suicidal behavior’, the number and percentage of subjects by items, with any suicidal behavior, and with no suicidal behavior will be summarized at baseline, each visit, entire DSP-5423(tablet) treatment period, and entire DSP-5423P application period.

Suicidal behavior

1. Any actual attempts

2. Any interrupted attempts
3. Any aborted attempts
4. Any preparatory acts or behavior

The number and percentage of subjects with either suicidal ideation or suicidal behavior as ‘any suicidality’, and with no suicidality will be summarized at baseline, each visit, entire DSP-5423(tablet) treatment period, and entire DSP-5423P application period.

The subjects* with ‘emergence of suicidal ideation’ defined as subjects without suicidal ideation at baseline, but not in post-baseline of DSP-5423P application period, subjects* with ‘serious emergence of suicidal ideation’ defined as subjects with ‘No’ in both item 4 and item 5**, but not in post-baseline of DSP-5423P application period, subjects* with ‘emergence of suicidal behavior’ defined as subjects with no suicidal behavior at baseline, but not in post-baseline of DSP-5423P application period, subjects* with “emergence of suicidality” defined as subjects with neither suicidal ideation nor suicidal behavior, but either/both in post-baseline of DSP-5423P application period, subjects with ‘any completed suicide’, will be summarized based on the number and percentages.

* Subject with ‘Yes’ at baseline are not included in the denominator of percentages.

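### The marked-abnormality laboratory counts and the three absolute QTc limits take no account of the patch-phase baseline, so an abnormality already present can be counted as a post-baseline finding

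*SAP*

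**What the plan says.** **Laboratory values.** SAP 9.12.2 defines the count: "The frequencies and percentages of subjects who met MAPLV at least once in the post-baseline of DSP-5423P (including unscheduled visits), will be presented". The Table 6 limits are absolute values or multiples of the upper limit of normal. HbA1c is marked at 7.5% or above, and serum prolactin at 5 times the upper limit or above.

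**Entry.** Protocol 8.2, criterion 8, excludes "Patients with an HbA1c level (NGSP level) of 8.4% or higher", so values from 7.5% to just under 8.4% are eligible. Treated diabetes at entry is foreseen in Protocol 10.3.4: "All drugs used for the treatment for complications (eg, hypertension, hyperlipidemia, diabetes) at screening should be continued without any dosage modification".

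**QTc.** SAP 9.12.4 says: "The number and percentage of subjects met have QTcB or QTcF criteria in Table 8 will be summarized". Table 8 has five rows. Three are absolute (above 450, 480 and 500 msec). Two are changes, of which the first is "Increased from baseline > 30 msec" and the second uses 60 msec. The eligibility criteria set no QTc limit.

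**Baseline.** Under SAP 8.4 the patch-phase baseline "is defined as the last non-missing data on or prior to Day 1". In Cohort 1 that point follows the 6-week tablet phase. SAP 8.4 also defines a separate Tab-Baseline.

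**Elsewhere in the plan.** For emergent suicidality, SAP 9.12.6 notes that subjects already positive "at baseline are not included in the denominator of percentages". Marked weight change (SAP Table 7) is a percentage change from baseline. Protocol 15.3.6.2 asks for a shift table from baseline to the highest score for DIEPSS items. Neither the SAP text nor its list of tables contains a shift table for laboratory or QTc categories.

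**The concern.** The primary objective is the safety of the patch over 52 weeks, and the study has no control arm. No comparator shows how many subjects would exceed a limit anyway. A count of subjects beyond a limit then mixes two groups: those who crossed it on the patch and those who were already beyond it when the patch started. Tables 14.3.4.7 (laboratory) and 14.3.6.4 (ECG) would give one figure for both.

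HbA1c is the clearest case, because the overlap follows from two printed limits and needs no assumption. Serum prolactin and QTc also matter, because both are named safety endpoints (SAP 7.2). In Cohort 1 the two safety outputs can also disagree. Under SAP 7.2.1, an adverse event that began on tablets and did not worsen on the patch belongs to the tablet period only. A laboratory value that did exactly the same can be counted in the patch-phase table.

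**Working it through.** The plan gives no figure on this point. Its only computed design figure is the enrolment target, which reproduces as 100 / (1 − 0.5) = 200 (Protocol 15.1) and is not in dispute.

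**Step 1: the overlap.** The marked limit is 7.5% and the exclusion limit is 8.4%. The eligible band already meeting the marked criterion is 7.5% to under 8.4%, a width of 8.4 − 7.5 = 0.9 percentage points.

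**Step 2: would a subject in the band be flagged?** SAP 8.5 lists 8 post-baseline laboratory visits (Weeks 2, 6, 12, 20, 28, 36, 44, 52), and one value is enough. Assume a constant true level μ, independent readings and within-subject SD s (assumed 0.1 to 0.3). The single-visit probability is p = 1 − Φ((7.5 − μ)/s). Over K visits it is 1 − (1 − p)^K.

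- μ = 7.5%: p = 0.5, so 1 − 0.5^8 = 0.996 over 8 visits and 1 − 0.5^2 = 0.75 over 2.
- μ = 7.8%, s = 0.3: p = 0.841, so 1 − 0.159^2 = 0.975 over 2 visits and practically 1 over 8.

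So most subjects who stay in the band are flagged, including many who leave early.

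**Step 3: effect on the reported percentage.** Let f be the share of patch-treated subjects who start in the band and stay there (all counted). Let g be the new-case rate among the others.

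Reported percentage = f + (1 − f)g. Carried-in share of the count = f / [f + (1 − f)g].

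| f | Reported, g = 1% | Carried-in share | Reported, g = 3% | Carried-in share |
|---|---|---|---|---|
| 0% | 1.00% | 0% | 3.00% | 0% |
| 1% | 1.99% | 50% | 3.97% | 25% |
| 3% | 3.97% | 76% | 5.91% | 51% |
| 5% | 5.95% | 84% | 7.85% | 64% |
| 10% | 10.90% | 92% | 12.70% | 79% |

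Example: f = 5%, g = 1% gives 0.05 + 0.95 × 0.01 = 0.0595, and 0.05 / 0.0595 = 84%. Restricting the count to subjects below the limit at baseline returns g itself, 1% or 3%, in every row. The shares do not depend on the number of subjects, so it does not matter that fewer than 200 may reach the patch phase.

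**Step 4: QTc.** Three of the five Table 8 rows have no baseline condition and two have one.

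**The case against.** The strongest reply is that the plan already does much of the separating.

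- Clinically significant laboratory and ECG abnormalities are recorded as adverse events (Protocol 12.2). Treatment-emergent events must start on or after Day 1 (SAP 9.12.1), and an event that began on tablets and did not worsen stays in the tablet period.
- Changes from baseline are summarised by visit, laboratory box plots include baseline, tablet-phase chemistry has its own summary, and all values are listed. A fall from 8.0% to 7.6% enters the change summary as a fall.
- Protocol 15.3.6.3 promises only by-visit statistics, so the marked-abnormality count is a descriptive addition. Its error runs towards overstating risk.

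All of this stands, and it limits the harm. It does not supply the missing number: by-visit changes describe groups, and the adverse event route depends on the investigator's judgement of significance.

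A reader might also infer more than the documents support.

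- *That every QTc count ignores baseline.* The 30 and 60 msec rows are increases from baseline.
- *That the QTc summary includes pre-treatment values.* The summary sentence does not say post-baseline, but the title of Table 14.3.6.4 does, and so does the next sentence, on the listing.
- *That the patch will be charged with a tablet effect on prolactin.* Protocol 7.2.2 says only that common tablet events, "including akathisia, tremors, insomnia, and increased blood prolactin, have been observed in 4 weeks after administration initiation". Nothing shows values reaching 5 times the upper limit. Both products contain the same active ingredient, so a rise that persists on the patch is not purely a tablet effect.
- *That the tables claim a drug effect.* They are titled post-baseline, not treatment-emergent.

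**Conclusion.** The point holds for the Table 6 counts, with HbA1c the clearest case, and for the three absolute QTc limits. An abnormality present at patch baseline, including one that arose in the Cohort 1 tablet phase, can be counted as a marked post-baseline abnormality even when the subject has improved. No planned table gives the number who newly cross a limit.

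The overlap is certain; its size is not. The documents give no baseline distribution of HbA1c, and screening eligibility does not fix the value at patch baseline. The carried-in shares of about 50% to 92% (1% new-case rate) and 25% to 79% (3%) rest on an assumed 1% to 10% of subjects starting in the band and staying there. A reader might conclude that most reported HbA1c cases will be carried in. That depends wholly on these inputs, and the share is zero if the band is empty. No comparable figure can be given for prolactin or QTc. The change is worth making because it is cheap and bears on the primary objective.

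**What to change.** In SAP 9.12.2 and 9.12.4, for each Table 6 criterion and each of the three absolute QTc limits:

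- Add the number and percentage of subjects who meet it post-baseline among those who have a patch-phase baseline value and do not meet it there. Use that group as the denominator.
- Keep the present all-subject count beside it.
- For Cohort 1, also show the count among subjects not meeting the criterion at Tab-Baseline.

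Tables 14.3.4.7 and 14.3.6.4 change accordingly. The 30 and 60 msec rows, the Table 6 limits and the entry criteria stay as they are.

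The cost is SAP wording and a few more lines in two tables, from data already collected. The denominator is slightly smaller and differs by criterion, so it must be printed on each line.

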9.12.3 Vital sign and body weight

BMI is calculated based on the height at Screening and weight at each visit.

Observed values and changes from baseline at DSP-5423P application period for the vital sign, weight and BMI will be summarized by visits including LOCF endpoints. The vital sign, weight and BMI will be listed.

Criteria for Markedly Abnormal Post-Baseline Vital Signs (MAPVS) for abnormal values in the vital sign can be found in Table 7. The frequencies and percentages of subjects who met MAPVS criteria at least once in the DSP-5423P post-baseline (including unscheduled visits) will be

presented. Weights for subjects with values met MAPVS criteria in DSP-5423P post-baseline period (including unscheduled visits) will be listed.

Table 7 Criteria for Markedly Abnormal Post-Baseline Vital Signs

Parameter	Unit	Markedly low	Markedly high
Weight	Kg	>= 7% decreased from baseline	>= 7% increased from baseline

Box plot of observed value of the vital sign, weight and BMI will be provided by visits including baseline at DSP-5423P application period and LOCF endpoint.

For DSP-5423(tablet) treatment period in Cohort 1, observed values and changes from baseline in DSP-5423(tablet) treatment period for the vital sign, weight and BMI will be summarized by visits including LOCF endpoints. Box plot of observed value of the vital sign, weight and BMI will be provided by visits including baseline of DSP-5423(tablet) treatment period for both DSP-5423(tablet) treatment period and DSP-5423P application period in Cohort 1.

9.12.4 12-lead ECGs

Observed values and changes from baseline in DSP-5423P treatment period for ECG parameters (RR interval, QT interval, PR interval, QRS interval, and QTc interval (QTc Fridericia [QTcF] and QTc Bazett [QTcB])) will be summarized by visits including LOCF endpoints. Interpretation, which is ‘Normal’, ‘Abnormal’, or ‘Not evaluable’, will be summarized based on the number and percentage of subjects by visits including LOCF endpoints. In case that finding are identified in a subject, and his/her interpretation is ‘Normal’, the subject will be summarized as ‘Normal’. The ECG parameters will be listed. The ECG parameters for subjects who experienced ‘Abnormal’ at least once in the DSP-5423P post-baseline (including unscheduled visits) will be listed.

The number and percentage of subjects met have QTcB or QTcF criteria in Table 8 will be summarized. The ECG parameters for subjects who met the criteria in Table 8 at least once in the DSP-5423P post-baseline (including unscheduled visits) will be listed.

Table 8 QT Prolongation

QTc Prolongation
QTc > 450 msec
QTc > 480 msec
QTc > 500 msec
Increased from baseline > 30 msec
Increased from baseline > 60 msec

For DSP-5423(tablet) treatment period in Cohort 1, observed values and changes from baseline in DSP-5423(tablet) treatment period for the ECG parameters will be summarized by visits including LOCF endpoints.

9.12.5 DIEPSS

Observed values and changes from baseline in DSP-5423P application period in DIEPSS total score excluding overall severity and item scores will be summarized by visits (including LOCF endpoint). The overtime change from baseline of DSP-5423P application period in DIEPSS total score excluding overall severity will be plotted for each cohort with +/-SD.

For DSP-5423(tablet) treatment period in Cohort 1, observed value and change from baseline in DSP-5423(tablet) treatment period in DIEPSS total score excluding overall severity and item scores will be summarized by visits. For both DSP-5423(tablet) and DSP-5423P periods in Cohort 1, the overtime change from baseline of DSP-5423(tablet) treatment period in DIEPSS total score excluding overall severity will be plotted with +/-SD.

DIEPSS total score and item scores will be listed.

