6.2 Safety endpoints

- 1) Adverse events (AEs) and adverse drug reaction (ADRs)
- 2) Extrapyramidal AEs and ADRs
- 3) Skin-related AEs and ADRs at the application site
- 4) Assessment of skin irritation reaction at the application site
- 5) Change in Drug-Induced Extrapyramidal Symptoms Scale (DIEPSS) Total Score (excluding overall severity) from baseline
- 6) Change in individual DIEPSS scores from baseline
- 7) Serum prolactin concentration
- 8) Electrocardiogram (ECG) parameters (QTc)
- 9) Concomitant use of antiparkinson drug

- 10) Assessment of suicides using Columbia-Suicide Severity Rating Scale(C-SSRS)
- 11) Laboratory test values, vital signs and body weight

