15.3.6.2 DIEPSS

- 1) Change from Baseline in DIEPSS total score (excluding overall severity)

Summary statistics will be calculated by visits.

- 2) Change from Baseline to DIEPSS item scores

For each item score, a shift table will be created based on the baseline to the highest scores per subjects.

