15.3.10.2 Analysis visit

All data will be organized and analyzed according to the scheduled timing as outlined in Table 2 and 3 Schedule of Assessments and according to the visit denoted in the CRFs. Unscheduled visits may not be used for any analysis unless otherwise specified. The data collected at the discontinuation visit within 7 days from the final application of study drug are mapped to the next scheduled visit of the actual discontinuation date and utilized for analysis.

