ECG	Electrocardiogram (ECG)
EDC	Electronic data capture (electronic information-gathering systems)
EQ-5D	EuroQol-5 Dimension
GCP	Good Clinical Practice (Good clinical study Practice)
γ-GTP	γ-glutamyl transpeptidase (Glutamyltranspeptidase)
HbA1c	Hemoglobin A1c (Hb A1c)
IPDs	Important protocol deviations (deviation from critical clinical study plans)
K	Potassium (K)
LDH	Lactate dehydrogenase (lactate dehydrogenase)
LLN	Lower limit of normal
LOCF	Last Observation Carried Forward
MAPLV	Markedly Abnormal Post-Baseline Laboratory Values
MAPVS	Markedly Abnormal Post-Baseline Vital Signs
MedDRA	Medical Dictionary for Regulatory Activities

Abbreviation	Full description
Na	Sodium (Na)
PANSS	Positive and Negative Syndrome Scale (Positive and Negative symptom Rating Scale)
PK-PD	Pharmacokinetics-Pharmacodynamics
PT	Preferred Term
QTc	QT interval corrected for heart rate (corrected QT)
QTcB	QTcB - Bazett's Correction Formula
QTcF	QTcF - Fridericia's Correction Formula
SD	Standard Deviation
SE	Standard Error
SOC	System Organ Class
TEAE	Treatment emergent adverse event
ULN	Upper limit of normal
WHO	World Health Organization

3. Change from analysis specified in study protocol

No changes were made.

4. Objective of the study

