8.5 Analysis Visit

Data of DSP-5423P treatment period is defined as the data captured on Day 1 through 7 days after the final application of DSP-5423P.

All data will be organized and analyzed according to the scheduled timing as outlined in Tables 1 and 2 Schedule of Assessments and according to the visit denoted in the CRFs. Unscheduled visits may not be used for any analysis unless otherwise specified. However, the data collected at the discontinuation visit within 7 days from the final application of study drug are mapped to the next scheduled visit of the actual discontinuation date. In listing, all data including unscheduled visit data should be presented.

1) CRF discontinuation visits in DSP-5423 (tablet) treatment period

Assessments and tests	Relative Day	Analysis Visit
PANSS, CGI-S, DIEPSS, body weight, body temperature, blood pressure, pulse rate	Tab-Day 1 to 11	Tab-W1, 2, 4, 6
	Tab-Day 12 to 18	Tab-W2, 4, 6
	Tab-Day 19 to 32	Tab-W4, 6
	Tab-Day 33 or later	Tab-W6
Laboratory test, ECG	Tab-Day 1 to 18	Tab-W2, 6
	Tab-Day 18 or later	Tab-W 6

The Tab-Day 1 is defined as the date of initial administration of DSP-5423 (tablet). CRF discontinuation visits in DSP-5423 (tablet) treatment period is defined as data on first non-missing (ex. no visit or results are missing) visit which meets all above requirements. Laboratory test and vital sign (body temperature, blood pressure, pulse rate) are performed visit handling for each item. Others are not considered as missing if they have any one component.

2) CRF discontinuation visits in DSP-5423P application period

Assessments and tests	Relative Day	Analysis Visit
PANSS, CGI-S, DIEPSS, C-SSRS,	Day 1 to 11	W1, 2, 4, 6, 8, 12, 16, 20, 24, 28, 36, 44, 52
	Day 12 to 18	W2, 4, 6, 8, 12, 16, 20, 24, 28, 36, 44, 52

Assessments and tests	Relative Day	Analysis Visit
Skin irritation assessment, body weight, body temperature, blood pressure, pulse rate	Day 19 to 32	W4, 6, 8, 12, 16, 20, 24, 28, 36, 44, 52
	Day 33 to 46	W6, 8, 12, 16, 20, 24, 28, 36, 44, 52
	Day 47 to 60	W8, 12, 16, 20, 24, 28, 36, 44, 52
	Day 61 to 92	W12, 16, 20, 24, 28, 36, 44, 52
	Day 93 to 120	W16, 20, 24, 28, 36, 44, 52
	Day 121 to 148	W20, 24, 28, 36, 44, 52
	Day 149 to 176	W24, 28, 36, 44, 52
	Day 177 to 204	W28, 36, 44, 52
	Day 205 to 267	W36, 44, 52
	Day 268 to 323	W44, 52
	Day 324 or later	W52
Laboratory test, ECG	Day 1 to 18	W2, 6, 12, 20, 28, 36, 44, 52
	Day 19 to 46	W6, 12, 20, 28, 36, 44, 52
	Day 47 to 92	W12, 20, 28, 36, 44, 52

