8.6 LOCF endpoint

The last observation from Day 1 through 7 days after the final application of DSP-5423P, except for baseline data defined in section 8.4, will be carried forward and will be defined as the Week 52 (LOCF).

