Table 14.3.6.1	Electrocardiogram Parameters – DSP-5423P Treatment Phase	Safety Population
Table 14.3.6.2	Electrocardiogram Parameters – DSP-5423 (tablet) Treatment Phase	Subjects treated with DSP-5423 (tablet)
Table 14.3.6.3	Electrocardiogram Abnormality – DSP-5423P Treatment Phase	Safety Population
Table 14.3.6.4	Markedly Abnormal Post-Baseline Values - Electrocardiogram – DSP-5423P Treatment Phase	Safety Population
Table 14.3.7.1	Drug-Induced Extrapyramidal Symptom Scale (DIEPSS) Total Score – DSP-5423P Treatment Phase	Safety Population
Table 14.3.7.2	Drug-Induced Extrapyramidal Symptom Scale (DIEPSS) Total Score – DSP-5423 (tablet) Treatment Phase	Subjects treated with DSP-5423 (tablet)
Table 14.3.7.3	Drug-Induced Extrapyramidal Symptom Scale (DIEPSS) Symptom Scores – DSP-5423P Treatment Phase	Safety Population
Table 14.3.7.4	Drug-Induced Extrapyramidal Symptom Scale (DIEPSS) Symptom Scores – DSP-5423 (tablet) Treatment Phase	Subjects treated with DSP-5423 (tablet)
Table 14.3.8.1	Columbia Suicide Severity Rating Scale (C-SSRS) Suicidal Ideation	Safety Population
Table 14.3.8.2	Columbia Suicide Severity Rating Scale (C-SSRS) Suicidal Behavior	Safety Population
Table 14.3.8.3	Columbia Suicide Severity Rating Scale (C-SSRS) Incidences of Suicidality	Safety Population
Table 14.3.8.4	Columbia Suicide Severity Rating Scale (C-SSRS) Emergence of Suicidality – DSP-5423P Treatment Phase	Safety Population
Table 14.3.9	Skin Irritation Assessment – DSP-5423P Treatment Phase	Safety Population
Table 14.4.1	Drug Attitude Inventory-10 (DAI-10) Total Score – DSP-5423P Treatment Phase	Safety Population

No	Title	Population
Table 14.4.2	Drug Attitude Inventory-10 (DAI-10) – DSP-5423P Treatment Phase	Safety Population
Table 14.4.3	Drug Attitude Inventory-10 (DAI-10) Total Score Compared to Baseline Assessment – DSP-5423P Treatment Phase	Safety Population
Table 14.4.4	EuroQol-5 Dimension (EQ-5D) Index Value – DSP-5423P Treatment Phase	Safety Population
Table 14.4.5	EuroQol-5 Dimension (EQ-5D) – DSP-5423P Treatment Phase	Safety Population
Table 14.4.6	Questionnaire for Formulation – DSP-5423P Treatment Phase	Safety Population
Table 14.5.1.1	Plasma Concentration of Blonanserin and Metabolites	PK Analysis Population
Table 14.5.1.2	Ratio of Plasma Concentration of Metabolites to Blonanserin	PK Analysis Population
Table 14.5.2.1	Plasma Concentration of Blonanserin and Metabolites by Sex	PK Analysis Population

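### SAP 9.12.5 drops the protocol's DIEPSS item shift table (baseline to highest score) without declaring it, and by-visit and LOCF summaries cannot replace it

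*SAP*

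**What the plan says.** Protocol 6.2 lists "Change in individual DIEPSS scores from baseline" among the safety endpoints, and SAP 7.2 repeats it. Protocol 15.3.6.2 gives two DIEPSS analyses: by-visit summary statistics for the change in total score and, for the items, "For each item score, a shift table will be created based on the baseline to the highest scores per subjects".

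SAP 9.12.5 plans, for observed values and changes from the DSP-5423P baseline, that "DIEPSS total score excluding overall severity and item scores will be summarized by visits (including LOCF endpoint"). It adds the same by-visit summaries for the tablet period of cohort 1, plots of the total score, and a listing. It mentions no shift table and no highest score. In SAP 10.2 the only item-level DIEPSS tables are 14.3.7.3 and 14.3.7.4, both titled "Drug-Induced Extrapyramidal Symptom Scale (DIEPSS) Symptom Scores" with the treatment phase added. SAP section 3, where departures from the protocol belong, says "No changes were made".

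Two data rules also matter. SAP 8.6 builds the LOCF endpoint from "The last observation from Day 1 through 7 days after the final application of DSP-5423P", excluding baseline. Protocol 15.3.10.2 states "Unscheduled visits may not be used for any analysis unless otherwise specified", and SAP 8.5 has the same rule.

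**The concern.** A baseline-to-highest shift table answers a subject-level question: how many people ever worsened on akathisia, tremor, rigidity and so on, from what starting score, and how far. By-visit means and a last-value endpoint answer a different one. The difference matters here because the protocol lets antiparkinson drugs be used when extrapyramidal symptoms appear (10.3.3.2) and lets the dose be reduced for adverse events (10.2). Item scores can therefore rise and then fall, and a last-value summary can miss that.

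A second, smaller gap sits behind the first. Protocol 10.2 calls for a DIEPSS rating when the dose is reduced because of extrapyramidal symptoms, and that can happen at an unscheduled visit. Under the default rule such a rating stays out of the by-visit tables. It would also stay out of a restored shift table unless an exception is written. The SAP writes that exception for markedly abnormal laboratory values (9.12.2) and weight (9.12.3), but not for DIEPSS.

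**Working it through.** **Step 1: set the texts side by side.**

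| Item | Protocol 15.3.6.2 | SAP 9.12.5 and 10.2 |
|---|---|---|
| Total score | Change, by visit | Observed value and change, by visit and LOCF |
| Item scores | Shift, baseline to subject's highest | Observed value and change, by visit and LOCF |
| Shift or highest-score output | Planned | None |
| Declared as a change (SAP 3) | – | No |

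The SAP does keep the protocol's other maximum-score analysis: skin irritation has a maximum in protocol 15.3.6.6 and in SAP 9.12.7. It also tabulates adverse events by maximum severity (9.12.1). The DIEPSS omission therefore looks like an oversight rather than a policy.

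**Step 2: can the planned summaries recover the table?** SAP 8.1 gives n, mean, SD, min, median and max. That maximum is taken across subjects at one visit, not across visits within a subject.

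Let c_v be the number of subjects above baseline on an item at visit v, with n subjects all present. The number who ever worsen is then known only to lie between max(c_v) and min(n, Σc_v).

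**Step 3: numerical illustration.** Inputs:
- 13 post-baseline DIEPSS visits (Weeks 1, 2, 4, 6, 8, 12, 16, 20, 24, 28, 36, 44, 52), from the schedule of assessments.
- Item range 0 to 4, from SAP 7.2.6.
- Assumed: 100 subjects, no missing visits, item baseline 0 for all, two subjects scoring 2 at each visit and the rest 0.

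In case A the two subjects differ at each visit. In case B they are the same two throughout. At every visit, and at LOCF, in both cases:
- mean = (2 × 2)/100 = 0.04
- SD = √[(2 × 2² − 100 × 0.04²)/99] = √(7.84/99) = 0.281
- min 0, median 0, max 2

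Baseline is 0, so changes equal observed values. Subjects shifting from 0 to 2:
- Case A: 13 × 2 = 26, or 26/100 = 26%, the upper bound from step 2.
- Case B: 2, or 2/100 = 2%, the lower bound.

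**Step 4: a second construction.** Take 200 subjects, all at baseline 0, with eight scoring 2 at each of the first 12 visits and everyone at 0 at Week 52. Both versions give mean (8 × 2)/200 = 0.08 and SD √[(8 × 4 − 200 × 0.08²)/199] = √(30.72/199) = 0.393 at those 12 visits. The Week 52 and LOCF means are 0. The shift from 0 to 2 is 8/200 = 4% if the eight are the same subjects and (12 × 8)/200 = 96/200 = 48% if they differ each time. Here LOCF shows no worsening in either version.

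**The case against.** The endpoint is not left unanalysed. The SAP summarises change in each item at every visit, which the protocol did not plan, and adds the tablet period. What is missing is one descriptive display in an uncontrolled study. Extrapyramidal adverse events are tabulated by term, maximum severity and first onset, and antiparkinson use by period. On unscheduled ratings, SAP 8.5 provides "In listing, all data including unscheduled visit data should be presented", so the table could be built later. All of this stands, and it limits the seriousness. It does not supply the omitted result: reported events are not the rated-item endpoint, and a listing is not a planned summary.

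The example is invented and extreme. It assumes no dropout, although protocol 15.1 expects about half of enrolled subjects to stop early. That is fair, and the percentages should be read only as proof that the summaries do not determine the table.

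SAP 8.1 also has a rule for categorical variables, no table shells are in the documents, and the item tables might show counts. Counts would not help: the full score distribution at each visit is identical in the paired cases.

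The two documents agree on unscheduled visits, so including those ratings goes beyond restoring the protocol's analysis. This is correct. Discontinuation ratings within 7 days of the last application are already mapped to a visit. The unscheduled exception is a recommendation, not a discrepancy.

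**Conclusion.** The concern holds. The protocol plans a per-item baseline-to-highest shift table, the SAP has none, and SAP section 3 says nothing changed. By-visit statistics, by-visit counts and LOCF cannot reproduce it: identical summaries are compatible with 2% or 26% of subjects ever worsening in one constructed case, and 4% or 48% in the other. Those figures rest on assumed data with full attendance and a baseline of 0, and say nothing about the expected rate. The omission follows from the texts alone.

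This should be corrected because a named safety endpoint loses its specified analysis in a safety study. It is not a threat to the study: the ratings are collected and listed, and other extrapyramidal outputs remain.

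**What to change.** 1. In SAP 9.12.5 and the table list in 10.2, add a shift table for each DIEPSS item: DSP-5423P baseline by highest post-baseline score, by cohort.
2. State that the highest score uses every rating after baseline through 7 days after the last application, including unscheduled and discontinuation visits. SAP 9.12.2 and 9.12.3 already count unscheduled values in this way. Mark this as an exception to the default in SAP 8.5.
3. Make SAP section 3 accurate. Once the table is restored, its statement is no longer wrong on this point. If the sponsor prefers to leave the table out, section 3 must say so and give the reason. Any other remaining departure from the protocol should be declared there too.

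The cost is one table and a few sentences, with no new data. The share of subjects who ever worsened can be larger than the share at any one visit, so the extrapyramidal picture may look less favourable than in the by-visit tables.
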